Currently available treatment options for these genitourinary symptoms of menopause (GSM) include use of lubricants with sexual intercourse, vaginal moisturizer a few times a week, twice weekly vaginal estrogen, a daily oral selective estrogen receptor modulator, or most recently vaginal dihydroepiandrosterone sulfate (DHEAS). All of these options require regular use of a medication, as a result several studies show high discontinuation rates of topical products⁷.

More recently, fractional carbon dioxide (fCO₂) laser treatment of the vaginal tissue has been proposed as a treatment for genitourinary symptoms of menopause. Laser treatment is a longstanding option for skin discoloration and scarring, and has been shown to induce collagen production and tissue remodeling⁸. Use of laser in gynecology presumes that vulvovaginal symptoms are due to the thinning of the vaginal mucosa and loss of underlying collagen that occurs with menopause. Examination of pre- and post-treatment vaginal biopsies shows a significant increase in vaginal mucosal thickness without damage to surrounding tissue^{9, 10}. Vaginal samples show an increase in lactobacillus colonization and decrease in pH¹¹. Case report and case series data suggest that the treatment is well tolerated by patients and is not associated with serious adverse events¹². Additionally, several case series demonstrate improvements in vulvovaginal^{13, 14} and urinary symptoms¹⁵, and in sexual function¹⁶.

However, these studies are from a select few centers, are small, and are also biased in that the laser treatment is only available to patients who are able to pay for it, although patients have reported that they found the cost worthwhile¹⁷. In addition, most studies report only on vulvovaginal symptoms, despite increasing use of laser for urinary symptoms. Several recent editorials have called for larger studies with longer follow-up and high quality outcome measures¹⁸⁻²⁰.

At Beaumont's Women's Urology and Pelvic Health Center, we have the unique opportunity to provide fractionated carbon dioxide laser vulvovaginal treatment for a wide range patients with vulvovaginal, sexual and urologic complaints.

Objectives and Outcomes

This study will evaluate the effect of fractional carbon dioxide laser therapy of the vagina in female patients with urogenital symptoms.

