Urogenital symptoms may include vaginal itching, burning, dryness, dyspareunia (difficult or painful sexual intercourse), dysuria (painful or difficult urination), nocturia (waking at night to urinate), incontinence (the involuntary loss of urine), urine frequency, urine urgency, and UTI.

Primary Objective	Evaluation of the subjective effects of fCO ₂ laser therapy on overall urogenital symptoms.
Secondary Objective	Assess vaginal pH and bacteria, overall vaginal health, urinary symptoms, sexual function, UTI frequency, and mental health status.
Primary Outcome	The mean and median response to treatment as measured by the Patient Global Impression of Improvement (PGI-I) questionnaire
Secondary Outcomes	Change in vaginal pH and overall vaginal health on physical examination as measured by the Vaginal Health Inventory Score (VHIS) Change in urinary symptoms as measured by the Questionnaire for Urinary Incontinence Diagnosis (QUID), OAB symptoms as measured by the Overactive Bladder Questionnaire-Short Form (OAB-q SF), cough stress test and voiding diaries Change in sexual function, including dyspareunia symptoms, as measured by the Female Sexual Function Inventory (FSFI) Change in the frequency of UTI occurrences Change in mental health status as measured by the Generalized Anxiety Disorder Questionnaire (GAD-7) and Patient Health Questionnaire (PHQ-8) Change in life and sexual impact of vulvovaginal skin symptoms as measured by the Incontinence Quality of Life Questionnaire (I-QOL) Change in the presence of lactobacillus, assessed by vaginal swab
Primary Endpoint	Week 16 (4 weeks post-treatment).
Secondary Endpoints	Primary and secondary outcomes will be evaluated again at Visit 4 (6-month follow-up) Primary and secondary outcomes will be evaluated again at Visit 10 (36-month follow-up)

SECTION II: METHODOLOGY

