This is a prospective observational study of patients undergoing vaginal treatment with the fCO₂ laser for various urogenital symptoms. We anticipate enrolling approximately 100 women in this study. The majority of patients are expected to be recruited from the WUC and private Urology offices. Informed consent will be obtained before any study activities are conducted. Women who meet all of the eligibility criteria will be enrolled in the study. Three treatments with the fCO₂ laser to the vagina will be performed, approximately six weeks apart. The patient will follow up every three months for the first year, then every six months for the following two years, for a total of three years of follow-up.

At each follow-up visit, the patients will complete specified questionnaires. The patient will be offered a repeat treatment at 1, 2 and 3 years if initial treatment efficacy has decreased. A pelvic examination will be performed at Visits 4 (6-month follow up), 6 (12-month follow up), 8 (24-month follow up), and 10 (36-month follow up) and the clinician will complete a cough stress test and the VHIS, including vaginal pH.

Patients will be advised to refrain from:

- vaginal intercourse for 24 hours prior to all visits.
- starting vaginal or systemic hormone therapy or use of new vaginal lubricants during the first six months of the study.
- starting any other preventative therapies for UTIs including antibiotic suppression, cranberry supplements, or d-mannose during the first six months of the study.
- starting any new treatments (i.e. pharmacologic, physical therapy) for overactive bladder (OAB) or stress urinary incontinence (SUI) during the first six months of the study.

Study patients will not be compensated for their participation in the trial. However, all research related activities, specified on the table of events, will be provided at no cost to the study patient.

Inclusion/Exclusion Criteria

Inclusion criteria:

- Female
- ≥18 years and ≤90 years of age
- One or more of the following indications for fCO₂ laser treatment:
 - Genitourinary symptoms of menopause, including after natural, medically-induced, or surgical menopause
 - Vaginal dryness, burning, itching, or dyspareunia not related to menopause
 - Recurrent UTIs, defined as 4 or more in a year
 - Overactive bladder
- Must sign the informed consent form
- Must be willing to comply with the study protocol

Exclusion criteria:

- Contraindications to fCO₂ laser treatment, such as:

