 - currently implanted synthetic pelvic mesh, sling, or tape
 - current or previous genital cancers
 - radiation to the vaginal or colo-rectal tissue
 - currently pregnant or less than 3 months following pregnancy
 - undiagnosed vaginal or cervical lesions

- Patients who have received vaginal fCO₂ laser treatment within the past 12 months
- Patients treated with vaginal estrogen within the past 3 months
- Patients with undiagnosed vaginal bleeding
- Active vulvar or vaginal infection, including herpes, candidiasis, etc.
- Current UTI, confirmed by positive urine culture and patient-reported UTI symptoms
- Pelvic or vaginal surgery within the past 9 months
- Pelvic organ prolapse beyond the introitus
- Patient possesses any other characteristics that, per the investigator's judgment, deems them unsuitable (i.e. may increase patient's risk, may affect the conduct of the study, etc.) for the treatment and/or study
- Participation in an investigational trial that used a study treatment, medication and/or biologic within 6 months or less prior to the date of the screening visit

Deferral

Patients may be deferred and rescreened at a later date under the following conditions:

- Patients with active vulvar or vaginal infections may be rescreened after treatment
- Patients with an active UTI may be rescreened after treatment
- Patients with undiagnosed vaginal bleeding may be rescreened after complete work-up, treatment and resolution of vaginal bleeding
- Patients pregnant within the past 3 months
- Patients who have received vaginal fCO₂ laser treatment within the past 12 months
- Patients treated with vaginal estrogen within the past 3 months
- Patients with recent pelvic or vaginal surgery within the past 9 months

Study Visits

Visit 0 – Baseline

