Laser treatment will be performed as per routine protocol. This includes intra-vaginal treatment based on atrophy level as based on VHIS score and treatment number.

Treatment	Atrophy	Treatment 1	Treatment 2	Treatment 3
Intravaginal	Severe (VHIS 6-15)	Energy: 7.5-10 mJ Density: 10%	Energy: 10 mJ Density: 10%	Energy: 10 mJ Density: 10%
	Moderate (VHIS 16-20)	Energy: 10 mJ Density: 10%	Energy: 10-12.5 mJ Density: 10-15%	Energy: 10-12.5 mJ Density: 10-15%
	Non-atrophic (VHIS >20)	Energy: 10 mJ Density: 10%	Energy: 12.5 mJ Density: 10-15%	Energy: 12.5 mJ Density: 15%

Laser is delivered at 6 points at each level of the vaginal wall: 12, 2, 4, 6, 8, and 10, o'clock of Hart's line. Delivery begins at the most proximal and the wand is retracted by 1 cm and another row of laser treatment is delivered. Number of levels is determined by patient vaginal length.

MEASURES

Cough Stress Test

During a vaginal exam, while the patient is in lithotomy or frog-legged position, the provider will ask the patient to cough and will look for visual signs of a urine leak. Any urine loss observed is indicative of a positive cough stress test.

Female Sexual Function Index (FSFI)

This validated questionnaire is a brief multidimensional scale for assessing sexual function in women. The scale has received initial psychometric evaluation, including studies of reliability, convergent validity, and discriminant validity²⁴.

Generalized Anxiety Disorder 7-item (GAD-7)

This validated questionnaire is used for screening for anxiety with good reliability with sensitivity of 89% and specificity of 82%, for use in clinical practice and in research²⁵.

Incontinence-Quality of Life (I-QOL)

This validated questionnaire is a commonly used self-report quality of life measure specific to urinary incontinence. This tool can be used to assess the impact of urinary problems and their treatment. The I-QOL has 22 questions with the following 3 subscales: avoid and limiting behaviors (items), psychosocial impacts (9 items), and social embarrassment (5 items). It is easily self-administered and takes about 5 minutes to complete.²³

Overactive Bladder Questionnaire-Short Form (OAB-q SF)

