This validated measure evaluates overactive bladder symptom severity and health related quality of life (Coyne, 2015). Statistically significant correlations have been found between the OAB-q SF scales and other patient reported outcomes instruments. For example, higher levels of depressive symptoms as measured by the Center for Epidemiologic Studies Depression Scale (CES-D) were linearly related to higher levels of Symptom Bother (r 0.31, P<0.0001) and lower levels of health related quality of life (HRQL) on the OAB-q SF (r 0.35, P<0.0001). Both the Symptom Bother and HRQL scales easily differentiated between controls without overactive bladder (OAB), continent patients with OAB and incontinent OAB patients (P<0.0001).

Patient Global Impression of Improvement (PGI-I)

The Patient Global Impression of Improvement (PGI-I) will be used to evaluate the patients' perceptions of overall improvement after treatment. The questionnaire has been validated in several urogenital conditions²¹⁻²³.

Personal Health Questionnaire Depression score (PHQ-8)

This validated questionnaire is used for monitoring depression severity and response to treatment and can be used to screen for depression in at-risk populations.

Perception of Monetary Value

The laser treatments will be provided at no cost to the study participants. This questionnaire will be completed at the primary endpoint (16 weeks) and the 12 month visit.

Questionnaire for Urinary Incontinence Diagnosis (QUID)

This validated measure is used to evaluate improvement in stress-predominant urinary incontinence in women undergoing non-surgical treatment. It has been found to be valid and responsive with internal consistency and acceptable psychometrics characteristics for use in clinical trials²⁴.

Vaginal Health Index Score (VHIS)

The VHIS is a tool, used by providers, to determine if vaginal atrophy is present. Providers perform a vaginal exam and give a score of 1-5 (abnormal to normal, respectively) on each of the following vaginal parameters: elasticity, secretion/fluid volume, vaginal pH, integrity of the epithelium, and lubrication/moisture of the vaginal wall. A VHIS score less than 15 is indicative of vaginal atrophy.

Visual Analog Scale (VAS) for Pain/Discomfort

Patients will record their average pain score during treatment from 0 (no pain) to 10 (most severe pain imaginable) on a Visual Analog Scale for pelvic pain and discomfort.

Visual Analog Scale (VAS) for Procedure Difficulty

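### The pre-visit instruction leaves existing lubricants and all moisturisers uncontrolled and unrecorded before exams whose VHIS scores secretion, moisture and pH

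*Combined protocol and SAP*

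**What the plan says.** The list of things patients are advised to refrain from (Section II: Methodology) has one item tied to visit timing: "vaginal intercourse for 24 hours prior to all visits". The item on vaginal products is tied to study time instead and advises against "starting vaginal or systemic hormone therapy or use of new vaginal lubricants during the first six months of the study". Under Exclusion criteria, the only topical vaginal product named is estrogen: "Patients treated with vaginal estrogen within the past 3 months". Moisturisers appear in no restriction and no exclusion.

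The background text expects such products in this population. It lists among current treatments "use of lubricants with sexual intercourse, vaginal moisturizer a few times a week", naming lubricants and moisturisers separately.

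Under Measures, the VHIS is scored 1 to 5 on each of "elasticity, secretion/fluid volume, vaginal pH, integrity of the epithelium, and lubrication/moisture of the vaginal wall". The Study Visits text places the VHIS and vaginal swab at Visits 1, 2, 3, 4, 6, 8 and 10. Change in VHIS, in vaginal pH and in lactobacillus are secondary outcomes, evaluated at Visit 4 and again at Visit 10. Section V says that changes in continuous measures to Visit 4 may be examined by paired t tests, with no comparison group. The Treatment section also uses the score to select laser settings: "This includes intra-vaginal treatment based on atrophy level as based on VHIS score and treatment number".

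**The concern.** The plan recognises that a recent vaginal exposure can matter at an exam, since it sets a 24-hour rule for intercourse. It sets none for products that are used to change vaginal moisture, although two VHIS items score wetness directly.

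Constant use before every exam would largely cancel in a within-woman change. Use need not be constant, because it plausibly follows dryness, which is one of the symptoms being treated. Suppose a product raises the score. A woman who improves and stops then has a product-assisted baseline and an unassisted Visit 4, so her benefit is understated. A woman who starts or increases use shows the opposite error. The advice on new lubricants ends at six months and does not clearly cover moisturisers at any time, so Visits 6, 8 and 10 are more exposed than Visit 4.

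With one arm, a shift of this kind cannot be separated from a treatment effect. Without a record of last use, it cannot be examined afterwards either.

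**Working it through.** The plan gives no figure for this point: no product effect, no usage rate and no VHIS standard deviation. There is nothing to reproduce, so the calculation below is illustrative.

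**Share of the scale exposed** (items and 1-5 scoring from Measures)
- Range of the total: 5 × 1 = 5 to 5 × 5 = 25, a span of 20 points.
- Secretion and moisture: 2 × 4 = 8 of 20 points.
- Adding pH: 3 × 4 = 12 of 20 points. The documents do not say which way a product would move pH.

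**Shift in mean VHIS change, baseline to Visit 4**

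Formula: proportion of users × probability of use in the 24 hours before an exam × proportion of users who stop by Visit 4 × points added by the product.

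Assumptions: users 0.30 to 0.50; use on 3 days in 7, one reading of the background's few times a week; half stop; 1 point (one item moves) to 3 points (all three items move up by one).
- Recent use at baseline: 0.30 × 3/7 = 0.129; 0.50 × 3/7 = 0.214.
- Half of these stop: 0.064; 0.107.
- At 1 point: 0.06 to 0.11.
- At 3 points: 0.19 to 0.32.

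The range is therefore about 0.06 to 0.32 points. In this scenario benefit is understated; if use rises instead, the sign reverses.

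**Laser rows** (row limits 6-15, 16-20 and above 20, from the Treatment table)
- A shift of 1 point in the total changes the row for true totals of 15 and 20.
- A shift of 3 points changes it for 13-15 and 18-20.

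Setting the rows side by side shows what a change of row does:
- Treatment 1: the two upper rows are identical (10 mJ, 10%), and the severe row (7.5-10 mJ, 10%) includes that setting.
- Treatments 2 and 3: the severe setting (10 mJ, 10%) lies within the moderate ranges (10-12.5 mJ, 10-15%).
- Treatments 2 and 3: the non-atrophic settings (12.5 mJ with 10-15%, then 12.5 mJ with 15%) also lie within the moderate ranges.

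Every adjacent pair of rows thus shares a permitted setting at every treatment, and a change of row need not change what is delivered.

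**The case against.** The strongest reply is that the plan already covers part of this and that little depends on the rest.
- The background describes lubricants as used with intercourse, so the 24-hour intercourse rule removes much of that use.
- The advice against new lubricants spans the period to Visit 4, and stable use partly cancels in a paired change.
- Current medications are reviewed at Visit 0 and Visits 2 to 10, which might pick up a product.
- Women may enrol for overactive bladder or recurrent UTI alone and need not use such products.
- VHIS is one of many secondary outcomes in a descriptive study.

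All of this stands, and it keeps the point small. It does not close the gap: moisturiser and non-coital lubricant use remain unrestricted before an exam, and a medication list does not show when a product was last applied.

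A reader might infer more than the documents support, in three ways:
- **That laser treatment would be mis-set.** The overlap between adjacent rows does not support this.
- **That the bias is 0.45 to 0.75 points** (0.30 to 0.50 × 0.5 × 3). That treats every user as having applied a product just before the exam, which does not fit use a few times a week.
- **That pH and lactobacillus results are distorted.** No section says that these products alter either one.

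The documents also do not show that 24 hours is long enough to clear a product.

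**Conclusion.** The point holds as a minor one. Recent use of an existing lubricant or any moisturiser is uncontrolled and unrecorded before exams that supply the VHIS and pH outcomes. In a single-arm before-after comparison, changing use cannot be told apart from treatment effect.

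The direction is not known. The size is not known either: about 0.06 to 0.32 VHIS points rests entirely on the assumed usage, timing, stopping rate and item effect. With no VHIS standard deviation in the documents, its importance relative to the expected change cannot be judged.

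A reader might take this as a threat to the study's main result. It is not, because the primary outcome is the PGI-I, given by phone about four weeks after the third treatment, and it does not use the VHIS.

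**What to change.** As a step to standardise measurement:
- For visits with a VHIS and swab (1-4, 6, 8 and 10), extend the existing 24-hour pre-visit instruction to non-prescribed vaginal lubricants and moisturisers.
- Add one CRF item for product type and time since last use. This also allows windows other than 24 hours to be examined.
- Repeat the VHIS and pH change summaries, and optionally lactobacillus, without exams that had use inside the window. Present this as a sensitivity summary beside the full one, because recent use may itself depend on symptoms.

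The cost is one line of patient instruction, one CRF item and one repeated summary. Regular users go one day without product before seven visits, and the repeated summary has slightly fewer pairs. No laser setting is proposed.

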A database will be created utilizing RedCap, MS Excel, or equivalent software. Only designated study personnel will have access to the database, which will be stored on the Urology Research Department's shared drive. Access to the computerized system will be password protected. To ensure accuracy of data entry, database entries will be cross-checked against source

documents. The shared drive is backed up nightly to ensure minimal data loss, even in the most catastrophic system failure. The database will be active until all study visits are completed, final monitoring activities have been conducted, and all data queries have been resolved. After that time, the database will be locked, prohibiting any changes to the data.

All study records, including both paper and electronic, will be stored in accordance with all federal and institutional requirements, including, but not limited to, the HIPAA Privacy Rule, the Food and Drug Act, and Medicare policy. The stored data will be kept in a secure, protected manner. All records will be retained, at a minimum, for eleven years beyond study completion.

SECTION V: STATISTICAL CONSIDERATIONS AND DATA ANALYSIS

This is a novel observational study without a comparison group. Therefore, a power calculation is not necessary. Descriptive statistics will be given for all data collected. Patients will be analyzed and described overall as a group, and subgroup analyses will be performed by presenting complaint(s). Missing data will be considered missing and no interpolations or substitutions will be performed. Categorical characteristics will be summarized using frequencies and percentages. Continuous characteristics will be summarized using mean and standard deviation for normally distributed variables and median and 25th and 75th percentiles for those not normally distributed. The changes in the continuous measures from baseline (prior to device implant) to Visit 4 may be examined using paired t tests. We will explore relationships within this group of patients with possible complications using appropriate methods. SAS for Windows version 9.3 Cary, NC or equivalent will be used for all analyses.

SECTION VI: REFERENCES

1. Nappi RE and Kokot-Kierepa M. Women's voices in the menopause: results from an international survey on vaginal atrophy. *Maturitas*. 2010; 67: 233-8.
2. Nappi RE and Palacios S. Impact of vulvovaginal atrophy on sexual health and quality of life at postmenopause. *Climacteric*. 2014; 17: 3-9.

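### For women enrolled on recurrent UTI, the qualifying year and the baseline UTI window are undefined; if they coincide, UTI frequency is expected to fall with no laser effect

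*Combined protocol and SAP*

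**What the plan says.** The Inclusion Criteria ask for "One or more of the following indications for" fCO₂ laser treatment. There are four, and the UTI indication reads "Recurrent UTIs, defined as 4 or more in a year". No calendar anchor follows. Other look-back criteria do carry one; the prior-laser exclusion, for example, covers "laser treatment within the past 12 months".

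Under Objectives and Outcomes, the secondary outcomes include "Change in the frequency of UTI occurrences". Outcomes are assessed again at Visit 4 and Visit 10. No section gives the baseline period for the UTI count, the follow-up period, or how infections between visits are counted.

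Section V states: "This is a novel observational study without a comparison group". On analysis it says: "The changes in the continuous measures from baseline (prior to device implant) to Visit 4 may be examined using paired t tests". It also plans subgroups by presenting complaint. The planned size is about 100 women, and the number expected to enter on the UTI indication is not given. Regression to the mean, a run-in and a second baseline count are not mentioned. The implant wording in the paired-test sentence does not fit a laser study, so the meaning of baseline needs settling there too.

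**The concern.** A woman's yearly UTI count varies by chance around her own underlying rate. Choosing women because a count reached 4 picks out some whose year was unusually bad, and their next year is on average closer to their usual rate. If change is measured from the count used to select them, that return appears as improvement. Without a control group, nothing in the data separates it from a laser effect.

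At stake is the UTI result in the women enrolled for recurrent UTI. The stated aim is to evaluate the effect of the laser, and reporting by presenting complaint would tend to display these women separately, where the artefact is least diluted.

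**Working it through.** **No figure to reproduce.** The plan gives no UTI rate, expected change or power, so this is a model check under assumptions.

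**Input from the protocol:** entry at a count X of 4 or more in a year; no control group.

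**Assumptions not in the documents:** each woman has a constant yearly rate drawn from a gamma distribution with mean μ and shape k; counts are Poisson given her rate; the laser has no effect; the qualifying year is the baseline; follow-up is one year.

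**Formulas.**
- X is negative binomial with mean μ and shape k.
- Baseline mean: B = E[X | X ≥ 4].
- Follow-up mean: F = (k + B) / (k/μ + 1).
- Fall: 1 − F/B.

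**Middle case, μ = 2, k = 2.**
- P(X = 0, 1, 2, 3) = 0.25, 0.25, 0.1875, 0.125, so P(X ≥ 4) = 1 − 0.8125 = 0.1875.
- Counts below 4 contribute 0.25 + 0.375 + 0.375 = 1.0 to the mean of 2, leaving 1.0 for counts of 4 or more.
- B = 1.0 / 0.1875 = 5.33.
- F = (2 + 5.33) / (2/2 + 1) = 3.67.
- Fall = 1 − 3.67/5.33 = 31%.

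**Main grid (baseline → follow-up, fall).**

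| μ | k = 1 | k = 2 | k = 4 |
|---|---|---|---|
| 2 | 6.00 → 4.67, 22% | 5.33 → 3.67, 31% | 4.96 → 2.99, 40% |
| 3 | 7.00 → 6.00, 14% | 6.08 → 4.85, 20% | 5.54 → 4.09, 26% |
| 4 | 8.00 → 7.20, 10% | 6.86 → 5.90, 14% | 6.19 → 5.09, 18% |

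Over μ from 1 to 6 and k from 0.5 to 5, the fall runs from 4% (μ = 6, k = 0.5) to 64% (μ = 1, k = 5). The direction is downward throughout.

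**Chance of a nominally significant fall.** If a paired t test were applied to one-year counts in the middle case, simulation gives p < 0.05 with a fall in 51% of samples of 10 women, 88% of 25 and 99% of 50. With 25 women, the range over the wider grid is 8% to 100%.

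**Missing anchor.** Suppose a count of 4 or more in any of the past five years qualifies (assumed look-back; μ 1 to 4, k 0.5 to 5).
- Worst year as baseline: fall of 31% to 66% (μ = 2, k = 2: 5.67 → 3.05, 46%).
- Most recent year as baseline: fall of 1% to 25% (μ = 2, k = 2: 3.26 → 3.05, 7%).

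**Whole cohort.** Let a share s enter on UTI at 5.33 → 3.67, with the others steady at an assumed 0.5 a year.
- s = 10%: 0.98 → 0.82, fall 17%.
- s = 25%: 1.71 → 1.29, fall 24%.
- s = 50%: 2.92 → 2.08, fall 29%.

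**Does an earlier year help?** With the criterion anchored to the 12 months before Visit 0, simulation of the middle case gives a mean of 3.66 for months 13 to 24 before, against 3.67 at follow-up. Under stable rates the artefact disappears.

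**The case against.** The strongest reply is that the plan never names the qualifying year as the baseline, and the artefact needs that step. This stands: the point is conditional, and the underlying gap is that the baseline count is undefined.

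A reader might infer that the unanchored year lets a woman's worst year serve as baseline and so must enlarge the bias. The documents do not support that. If the baseline is a recent year that need not be the qualifying one, the missing anchor shrinks the artefact, in some scenarios almost to nothing.

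A reader might also infer that the whole UTI result, or the trial's main result, is an artefact. Recurrent UTI is only one of four indications, UTI frequency is one of several secondary outcomes, and PGI-I is not affected by this mechanism. Nor need the presenting-complaint subgroup match the women who met the UTI criterion.

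Finally, the study calls itself observational, admits it has no comparison group, and is mainly descriptive. Paired tests are optional, limited to continuous measures up to Visit 4, and not specified for UTI counts, so the significance figures are illustrative. This tempers the point without removing it: a descriptive fall from a selected baseline still misleads in a study meant to evaluate the laser's effect. The advice against starting other UTI prevention in the first six months deals with co-intervention and leaves regression to the mean untouched.

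**Conclusion.** The concern holds in conditional form. If the qualifying year is the baseline, which is a natural reading of an undefined window, women entering on the UTI indication are expected to show fewer UTIs with no laser effect. Under the stated gamma-Poisson assumptions the fall is about 10% to 40% on the main grid and 4% to 64% on the wider one. The documents cannot say where in that range this population lies: it is small if most source patients have persistently high rates and large if they do not. The plan should be changed on this point, but the fault is confined to one secondary outcome in one group of women and does not undermine the primary analysis.

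**What to change.** 1. State that the UTI criterion and the baseline UTI count both refer to the 12 months before Visit 0.
2. At Visit 0, also record the UTI count for months 13 to 24 before, from the records and history already being taken.
3. For women entering on UTI, report the follow-up rate against both periods over windows of equal length, separately from other women. The comparison with months 13 to 24 is the check on regression to the mean. Visit 4 falls only about six months after the first treatment, so the window used there needs stating.
4. State in Section V that a fall against the qualifying year alone is not evidence of a laser effect.

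Steps 1 and 2 belong together: anchoring alone makes the qualifying year the baseline and could introduce the bias where it might otherwise have been small.

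The cost is one extra history item and some wording. The earlier count is a fair comparator only if rates were stable; recent onset of recurrence or different treatment at that time would distort it. Under-recall of the older year would understate the comparator and could hide a true fall, which is why it should stand beside the qualifying-year comparison and not replace it. The reported reduction may also look less favourable.
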